#### 20. DATA NOT SUMMARIZED OR PRESENTED

The other variables and/or domains not summarized are:

Comments

These domains and/or variables will not be summarized but will be available in the clinical study database and Study Data Tabulation Model (SDTM) datasets.

Document: \\quintiles.net\enterprise\Apps\sasdata\SASb\SAS\Arena\APD334\RZA28116\Biostatistics\Documenta

tion\SAP\503-Final SAP v2.0\APD334-203\_SAP\_Final v2.0-20231120\_clean.docx

Author: PPD Version Number: 2.0

Version Date: 20Nov2023

Template No.: CS\_TP\_BS016 Revision 7 Reference: CS\_WI\_BS005

Effective Date: 01Nov2021

Page 55 of 70

#### APPENDIX 1. Programming Conventions for Outputs

## IQVIA Output Conventions

Outputs will be presented as shown in the Output shells.

#### Decimals, Percentages and CI

- If the original data has N decimal places, then the summary statistics should have the following decimal places:
  - Minimum and maximum: N
  - Mean (and LS Means), median: N+1
  - SD or SE: N + 2
  - o CI: 2
- Percentages will be reported to one decimal place. Where counts are zero, percentages will not appear in the output.

#### Conventions Related to Pharmacokinetic Data

All etrasimod concentrations will be reported and analyzed with the same precision as the source data provided by the bioanalytical laboratory regardless of how many significant figures or decimals the data carry. The derived PK data (etrasimod concentration) will be rounded to carry 3 significant digits and considered the source data for the calculation of descriptive statistics and the statistical analysis source data.

For the reporting of descriptive statistics, the mean, geometric mean, median, SD, % CV, and geometric %CV will be presented with 4 significant digits. The minimum and maximum will be presented with 3 significant digits.

#### Dates & Times

Depending on data available, dates and times will take the form DDMMMYYYY or DDMMMYYYY:hh:mm.

Document: \quintiles.net\enterprise\Apps\sasdata\SASb\SAS\Arena\APD334\RZA28116\Biostatistics\Documenta

[figure not shown]
tion\SAP\503-Final SAP v2.0\APD334-203\_SAP\_Final v2.0-20231120\_clean.docx

Author: PPD Version Number: 2.0

Version Date: 20Nov2023

Template No.: CS\_TP\_BS016 Revision 7 Reference: CS\_WI\_BS005

Effective Date: 01Nov2021

Page 57 of 70

## **Spelling Format**

English US.

#### Presentation of Treatment Groups

For outputs, treatment groups will be represented as follows and in the given order:

Treatment Group	For Tables, Graphs and Listings
Etrasimod Totala	Etrasimod 2 mg and Etrasimod 1 mg
Etrasimod 2 mg	Etrasimod 2 mg
Etrasimod 1 mg	Etrasimod 1 mg
Placebo	Placebo
Screen Failure	Screen Failure
Not Treated a	Not Treated

a To be only used for AE tables.

# Presentation of Visits and Study Period

For outputs, visits and study periods will be represented as follows and in that order:

Visit Name	Study Period
Screening	Screening
Baseline, Day 1, Day 2, Week 2, Week 4, Week 8, Week 12	Treatment
End of Study/Early Termination	Depend on Analysis Visit assigned, described in Section 6.4
2-Week Follow-Up, 4-Week Follow-Up	Follow-Up

#### Listings

All listings will be ordered by the following (unless otherwise indicated in the template):

Randomized treatment group (or treatment received if it is a safety output), first by Etrasimod 2 mg, Etrasimod

Document: \quintiles.net\enterprise\Apps\sasdata\SASb\SAS\Arena\APD334\RZA28116\Biostatistics\Documenta

tion\SAP\503-Final SAP v2.0\APD334-203\_SAP\_Final v2.0-20231120\_clean.docx

Author: PPD Version Number: 2.0

Version Date: 20Nov2023

Template No.: CS\_TP\_BS016 Revision 7 Reference: CS\_WI\_BS005

Effective Date: 01Nov2021

Page 58 of 70

1 mg, then Placebo, then Screen Failure)

- Subject number (which is expected to incorporate study site/center)
- Date (where applicable)

Document: \\quintiles.net\enterprise\Apps\sasdata\SASb\SAS\Arena\APD334\RZA28116\Biostatistics\Documenta

tion\SAP\503-Final SAP v2.0\APD334-203 SAP Final v2.0-20231120 clean.docx

Author: PPD Version Number: 2.0

Version Date: 20Nov2023

Template No.: CS\_TP\_BS016 Revision 7 Reference: CS\_WI\_BS005

Effective Date: 01Nov2021

PROTOCOL APD334-203

Statistical Analysis Plan

Page 59 of 70

## APPENDIX 2. PARTIAL DATE CONVENTIONS

Imputed dates will NOT be presented in the listings.

#### Incomplete Start Dates for Adverse Events:

In case the start date of an AE is completely missing, or the start date is in the same year as the date of study drug administration (when only year is recorded), or the start date is in the same month and year (if only the day is missing) as the date of first study drug administration, then the start date of the AE will be imputed by the minimum of the date of first study drug administration and the AE end date. In all other cases the missing start day will be imputed by the 1st and the missing start month will be replaced by January.

#### Algorithm for Treatment Emergence of Adverse Events:

AE Start Date	AE Stop Date	Action
Known	Known, Partial or Missing	If AE start date < study treatment first dose date, then not TEAE  If AE start date ≥ study treatment first dose date, then TEAE
Partial, but known components show that it cannot be on or after date of first dose of study treatment	Known, Partial or Missing	Not TEAE
Partial, could be on or after date of first dose	Known	If AE stop date < study treatment first dose date, then not TEAE  If AE stop date ≥ study treatment first dose date, then TEAE
of study treatment OR Missing	Partial	Impute AE stop date as latest possible date (ie, last day of month if day unknown or 31st December if day and month are unknown), then:  If AE stop date < study treatment first dose date, then not TEAE  If AE stop date ≥ study treatment first dose date, then TEAE
	Missing	Assumed TEAE

Document: \quintiles.net\enterprise\Apps\sasdata\SASb\SAS\Arena\APD334\RZA28116\Biostatistics\Documenta

tion\SAP\503-Final SAP v2.0\APD334-203\_SAP\_Final v2.0-20231120\_clean.docx

Author: PPD Version Number: 2.0

Version Date: 20Nov2023

Template No.: CS\_TP\_BS016 Revision 7 Reference: CS\_WI\_BS005

Effective Date: 01Nov2021

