9.9.8.1.5. Severity

The severity of each adverse event will be assessed at the onset by a nurse/or physician. When recording the outcome of the adverse event the maximum severity of the adverse event experienced will also be recorded. The severity of each adverse event will be graded according to the Common Terminology Criteria for Adverse Events, version 5.0 (CTCAE v5.0):

Grade 1:	Mild; asymptomatic or mild symptoms; clinical or diagnostic observations only; intervention not indicated.
Grade 2:	Moderate; minimal, local or noninvasive intervention indicated; limiting age-appropriate instrumental activities of daily living (ADL).
Grade 3:	Severe or medically significant but not immediately life-threatening; hospitalization or prolongation of hospitalization indicated; disabling, limiting self-care ADL (eg, preparing meals, shopping for groceries or clothes, using the telephone, managing money)
Grade 4:	Life-threatening consequences, urgent intervention indicated.
Grade 5:	Death related to adverse event

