9.9.8.2.2. Recording Adverse Events

The adverse event reporting period for safety surveillance begins when the participant is initially included in the study (date of first signature of informed consent) and continues up to 30 days after the last administration of study treatment. If an adverse event is not resolved or stabilized by this time, the Sponsor in consultation with the Investigator will decide whether to continue to monitor the adverse event or closeout the event in the database if no further follow-up is necessary.

Investigators are not obligated to actively seek information on AEs or SAEs after the participant has concluded study participation. Any SAE suspected to be related to the study treatment must be reported whenever it occurs, irrespective of the time elapsed since the last administration of study treatment.

Investigators and study personnel will record all adverse events and SAEs whether received through an unsolicited report by a participant, elicited during participant questioning, discovered during physical examination, laboratory testing, and/or other means by recording them on the eCRF and/or SAE Form, as appropriate. The following information should be recorded on the adverse event eCRF:

- Description including onset and resolution dates
- Whether it met SAE criteria
- Severity
- Relationship to study treatment or other causality
- Outcome

For SAEs, events occurring secondary to the primary event should be captured and reported via the established safety reporting mechanism. .

The following should be considered when recording SAEs:

- Death is an outcome of an event. The event that resulted in the death should be recorded and reported on the eCRF.
- For hospitalizations, surgical, or diagnostic procedures, the illness leading to the surgical or diagnostic procedure should be recorded as the SAE, not the procedure itself. The

procedure should be captured in the narrative as part of the action taken in response to the illness.

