#### 18.1. Adverse Events

AEs will be coded using MedDRA (v24.1 or higher). The version used to code AEs will be displayed in the analyses. Treatment emergent adverse events (TEAEs) are defined as AEs that started or worsened in severity on or after the first dose of study treatment.

Refer to APPENDIX 2 for handling of partial dates for AEs for the purpose of assigning treatment-emergent flags. In the case where it is not possible to define an AE as treatment emergent or not, the AE will be classified as treatment emergent.

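### The treatment-emergent algorithm in SAP Appendix 2 has no test for worsening, so it contradicts the SAP's own definition for adverse events with a pre-dose start that worsen on treatment

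*SAP*

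**What the plan says.** **Definition.** SAP Section 18.1 has TEAEs "defined as AEs that started or worsened in severity on or after the first dose of study treatment". Onset and worsening are alternatives; either is enough.

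**Where the flag is set.** The same section continues: "Refer to APPENDIX 2 for handling of partial dates for AEs for the purpose of assigning treatment-emergent flags". It adds a default: where "it is not possible to define an AE as treatment emergent or not", the event is counted as treatment-emergent.

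**Algorithm.** The Appendix 2 table on treatment emergence takes the AE start date and stop date as its only inputs. For a known start date the rule is "If AE start date < study treatment first dose date, then not TEAE", whatever the stop date. The next row covers start dates described as "Partial, but known components show that it cannot be on or after date of first dose of study treatment", and the result is again not a TEAE, whatever the stop date. Severity appears in no row.

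**Data collected.** Protocol Section 9.9.8.2.2 starts AE recording at the first signature of informed consent. The eCRF items it lists include onset and resolution dates and severity, but no date of a severity change. Protocol Section 9.9.8.1.5 has severity assessed at onset and says that "the maximum severity of the adverse event experienced will also be recorded".

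**Reporting.** The AE summaries in SAP Sections 18.1.1 to 18.1.6 are of TEAEs. AEs that are not TEAEs appear in the general AE listing described in Section 18.1.1.

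**The concern.** A programmer who follows Appendix 2 will not implement the definition in Section 18.1. Take an AE that starts in screening at Grade 1, is ongoing at first dose and reaches Grade 3 in the treatment period. By the definition it is a TEAE; by the algorithm it is not.

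If that event sits on one AE record, it drops out of the tables by system organ class and preferred term, maximum severity, relationship, seriousness, discontinuation and special interest, and out of the exposure-adjusted incidence rate (EAIR) and the overview. It also drops out of the dedicated listings of serious TEAEs, TEAEs leading to discontinuation and TEAEs leading to death. SAP Section 18.2 sends death information to that last listing.

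This runs against the cautious direction of the SAP's other conventions: missing severity is tabulated as Grade 3, missing relationship as related, and missing seriousness as serious.

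**Working it through.** No stated figure depends on this point, so there is none to reproduce. The check sets the two rules side by side over every start-date state in the Appendix 2 table.

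**Inputs.** The definition comes from SAP Section 18.1 and the algorithm from SAP Appendix 2. An event that stopped before first dose cannot have worsened on or after it. The cases with worsening therefore have a stop date on or after first dose, or a missing one.

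| Start date | Stop date | Worsened on or after first dose | Section 18.1 | Appendix 2 |
|---|---|---|---|---|
| Known, before first dose | On/after first dose | Yes | TEAE | Not TEAE |
| Known, before first dose | Missing | Yes | TEAE | Not TEAE |
| Partial, must be before first dose | On/after first dose | Yes | TEAE | Not TEAE |
| Partial, must be before first dose | Missing | Yes | TEAE | Not TEAE |
| Either of the two above | Any | No | Not TEAE | Not TEAE |
| Known, on/after first dose | On/after first dose or missing | Yes or no | TEAE | TEAE |
| Ambiguous or missing | On/after first dose or missing | Yes or no | Cannot be settled from dates | TEAE |
| Ambiguous or missing | Before first dose | No | Cannot be settled from dates | Not TEAE |

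**Count.** Pre-dose start with on-treatment worsening gives 2 start-date states × 2 stop-date states = 4 configurations. The rules disagree in 4 of 4, and in no other row where the definition gives an answer.

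**Does the default rescue these events?** No. It applies where classification is impossible, and the table classifies these events outright.

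**Can such events occur?** Yes. AEs are recorded from consent, and Protocol Section 9.3 allows a 28-day screening period that can be extended.

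**Does the record structure avoid the conflict?** Only if a worsening is entered as a new AE with its own start date. Neither document says that. Onset severity plus one maximum for the same event points towards a single record.

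**Size.** The documents give no rate of screening-onset AEs and no rate of worsening, so no figure follows.

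**The case against.** **Appendix 2 handles partial dates only, so Section 18.1 governs complete dates.** The appendix title and the cross-reference both speak of partial dates. But the first row of the table is for start dates that are known, so it classifies complete dates too. This does not stand.

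**A worsening may be a new record.** Protocol Section 9.9.8.1.1 counts preexisting conditions that worsen as AEs, and SAP Section 18.1.1.1 plans for a TEAE reported more than once under the same term. If sites entered each worsening as a new AE, the two rules would agree. Neither passage sets that rule for an AE already recorded in screening, but neither excludes the practice, and the eCRF completion instructions are not among the documents. This stands as a condition: the loss occurs only when the worsening stays on the original record.

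**Other safety data are unaffected.** Laboratory, ECG, vital sign and pulmonary function summaries do not use the TEAE flag, so a worsening visible there would still be seen. This stands, but it does not repair the AE tables.

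**Stronger readings the documents do not support.**
- A reader might infer that every AE beginning before first dose is discarded. It is not: an event with an ambiguous or missing start is kept as a TEAE unless it stopped before first dose, and all AEs stay in the general listing.
- A reader might infer that on-treatment harm is shown to be understated. It is not shown, because the effect depends on recording practice.
- A reader might apply an assumed percentage to the planned 32 per arm. The documents supply no such percentage, and SAP Section 7 says that actual enrolment will be smaller. A lost event is also not a lost participant: anyone with another TEAE still counts in overall incidence, and Protocol Section 3.2 reports TEAEs in 50.0% to 59.6% of participants per group in the earlier Phase 2 study.

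**Conclusion.** The inconsistency is real and is wrong as written. For AEs whose start is known, or can be shown, to precede first dose, Appendix 2 returns a result contrary to the Section 18.1 definition whenever the event worsened on treatment (4 of 4 configurations). The consequence is conditional. If the worsening is kept on the original record, the event is missing from the TEAE tables and TEAE-specific listings and remains only in the general AE listing.

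Confidence is high in the textual conflict. How many events are affected, if any, cannot be derived from the documents. The conclusion rests on two assumptions: that programmers follow the Appendix 2 table as written, and that no instruction outside the two documents makes each worsening a new AE record.

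**What to change.** 1. **Add a branch to Appendix 2.** An AE with a start before first dose whose severity increased on or after first dose is a TEAE.
2. **Cover undated worsening.** The protocol's maximum severity carries no date. Where it exceeds onset severity, the event had not resolved before first dose and the timing of the worsening is unknown, apply the existing Section 18.1 default and flag the event as a TEAE.
3. **Align the EAIR.** Section 18.1.1 measures time from first dose to onset, which would be negative for these events. Use the date of worsening as the onset or, if that is unknown, the date of first dose.
4. **Query the existing records before unblinding.** Review AEs with screening onset that were ongoing at first dose and whose maximum severity exceeds onset severity, and obtain the date of worsening where possible. A new site instruction alone would not recover events already entered.

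The cost is a short SAP edit and a small data check. The downside is a possible slight over-count, since an event that peaked in screening and was settling at first dose would be flagged under step 2 if its timing could not be established.

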**IIQVIA** 

Page 60 of 70

## Algorithm for Prior / Concomitant Medications:

Start Date	Stop Date	Action
Known	Known	If medication stop date < study treatment first dose date, assign as prior If medication stop date ≥ study treatment first dose date, assign as concomitant
	Partial	Impute stop date as latest possible date (ie, last day of month if day unknown or 31st December if day and month are unknown), then:  If medication stop date < study treatment first dose date, assign as prior If medication stop date ≥ study treatment first dose date, assign as concomitant
	Missing	If medication stop date is missing could never be assumed a prior medication, assign as concomitant
Partial	Known	Impute start date as earliest possible date (ie, first day of month if day unknown or 1st January if day and month are unknown), then:  If medication stop date < study treatment first dose date, assign as prior If medication stop date ≥ study treatment first dose date, assign as concomitant
	Partial	Impute start date as earliest possible date (ie, first day of month if day unknown or 1st January if day and month are unknown) and impute stop date as latest possible date (ie, last day of month if day unknown or 31st December if day and month are unknown), then:  If medication stop date < study treatment first dose date, assign as prior If medication stop date ≥ study treatment first dose date, assign as concomitant
	Missing	Impute start date as earliest possible date (ie, first day of month if day unknown or 1st January if day and month are unknown), then:  If medication stop date is missing could never be assumed a prior medication, assign as concomitant
Missing	Known	If medication stop date < study treatment first dose date, assign as prior Else assign as concomitant
	Partia1	Impute stop date as latest possible date (ie, last day of month if day unknown or 31st December if day and month are unknown), then:  If medication stop date < study treatment first dose date, assign as prior  If medication stop date ≥ study treatment first dose date, assign as concomitant
	Missing	Assign as concomitant

\\quintiles.net\enterprise\Apps\sasdata\SASb\SAS\Arena\APD334\RZA28116\Biostatistics\Documenta Document:

tion\SAP\503-Final SAP v2.0\APD334-203 SAP Final v2.0-20231120 clean.docx

2.0 Author: Version Number: PPD

> Version Date: 20Nov2023

Template No.: CS\_TP\_BS016 Revision 7 Reference: CS\_WI\_BS005

Effective Date: 01Nov2021

Page 61 of 70

# Algorithm for Starting Date of Hospitalization and Start/Stop Dates of Concomitant Medications:

Start Date	Stop Date	Action
Partia1	Partial	Impute start date as earliest possible date (ie, first day of month if day unknown or 1st January if day and month are unknown). Impute stop date to latest possible date (ie, last day of month if day unknown or 31st December if day and month are unknown).  No partial stop date imputation for hospitalization.
Missing	Missing	Impute start date as informed consent date. Impute stop date as last visit date when the concomitant medication timepoint is not ongoing.  No missing stop date imputation for hospitalization.

Document: \\quintiles.net\enterprise\Apps\sasdata\SASb\SAS\Arena\APD334\RZA28116\Biostatistics\Documenta

tion\SAP\503-Final SAP v2.0\APD334-203\_SAP\_Final v2.0-20231120\_clean.docx

Author: PPD Version Number: 2.0

Version Date: 20Nov2023

Template No.: CS\_TP\_BS016 Revision 7 Reference: CS\_WI\_BS005

Effective Date: 01Nov2021

[figure not shown]

Page 62 of 70

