# 8.3. Missing Data

Missing adverse event (AE) relationship to study treatment and AE seriousness will be imputed as described in Section 18.1.1.2 and Section 18.1.3, respectively. Partial or missing AE start dates, concomitant medication (CM) start dates, and hospitalization dates will also be imputed as described in APPENDIX 2. No other missing safety data will be imputed.

Missing efficacy data will be handled as described in Sections 16.1.2, 16.2.2, 16.3.2. In the primary analysis of the primary endpoint and main analyses of all binary responder-type endpoints, all participants with missing data, regardless of reason for missingness, will be considered as non-responders. In the main analysis of continuous or score endpoints, such as biomarker measures and health-related quality of life measures, participants with missing data will be analysed with their observed data only, a mixed-effect model with repeated measures or analysis of covariance (ANCOVA).

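### Do the SAP's start-date imputation rules for medications and hospitalisations need a floor at first dose, as the adverse event rule has?

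*SAP*

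**What the plan says.** SAP Section 8.3 brings these dates into scope: "concomitant medication (CM) start dates, and hospitalization dates will also be imputed as described in APPENDIX 2". Appendix 2 then uses three conventions.

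- **Adverse event starts.** If the start is wholly missing, or its known parts match the first-dose month or year, the "start date of the AE will be imputed by the minimum of the date of first study drug administration" and the event's end date. Otherwise, "In all other cases the missing start day will be imputed by the 1st", and a missing month becomes January.
- **Medication and hospitalisation starts.** The last table in the appendix has one row for partial start with partial stop and one for missing start with missing stop. In the first the rule is "Impute start date as earliest possible date (ie, first day of month if day unknown or 1st January if day and month are unknown"). In the second it is "Impute start date as informed consent date". Medication stops go to the latest possible date, or to the last visit if missing and not ongoing. Hospitalisation stops are not imputed.
- **Prior or concomitant status.** A separate table also sets partial medication starts to the earliest date, but the label turns on the stop: "If medication stop date < study treatment first dose date, assign as prior". A missing stop gives concomitant.

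The appendix also states: "Imputed dates will NOT be presented in the listings".

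**The concern.** Within one appendix, two rules can date the same clinical event differently. UC-related admissions are captured on the adverse events form (SAP Section 17.1.3). Suppose first dose was on 10 March, the onset and the admission are both recorded only as March, and the event ended later. The event is dated 10 March and is treatment-emergent. Its admission is dated 1 March, before both the event and first dose.

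The stakes could be real. Under SAP Section 16.1.2, starting or increasing a UC medication makes a participant a non-responder in the primary and secondary analyses. Appendix 5 judges several drug classes on an increase from baseline after first dose. If a new course were dated before first dose, it might be read as background treatment and the intercurrent event missed. Section 17 analyses the proportion with concomitant UC-related hospitalisation, and an admission moved before first dose might drop out of that count. Because imputed dates are not listed, such a shift would not be visible in the listings.

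**Working it through.** The plan states no figure on this point, so there is none to reproduce. The check applies the rules to dates and then traces where an imputed start could be used.

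**Rules side by side.** Example: first dose 15 June 2022, consent assumed 28 days earlier (18 May), no event ending before first dose.

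| Recorded start | Adverse event rule | Medication/hospitalisation rule |
|---|---|---|
| May 2022 | 1 May | 1 May |
| June 2022 | 15 June | 1 June |
| July 2022 | 1 July | 1 July |
| 2022 only | 15 June | 1 January |
| missing | 15 June | 18 May |

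The rules differ only where the known parts leave an on-treatment start possible but unproven.

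**How often a true on-treatment start moves before first dose.** All 1,461 first-dose dates in 2021–2024 were enumerated, with true starts uniform over the days shown. A start moves if the imputed date (1st of the start month, or 1 January of the start year) is earlier than first dose.

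| True start | Day missing | Day and month missing |
|---|---|---|
| Days 2–85 | 16.4% | 88.1% |
| Days 2–57 | 24.6% | 91.9% |
| Days 58–85 | 0.0% | 80.4% |

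A wholly missing start always moves in the missing/missing row, because consent precedes dosing. These are shares of incomplete dates, not of participants. The documents do not give the number of incomplete dates.

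**Could a moved start pass for background treatment?**

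- *Oral corticosteroid.* Protocol Section 4.1 requires a stable dose for 4 weeks before the screening endoscopy. That endoscopy precedes randomisation, and central reading takes about 5 to 12 days (Table 6 footnotes). Compliant background use therefore began about 28 + 5 = 33 days or more before first dose. A day-missing start moves back at most 29 days before first dose. It reaches 28 days in 0.08% of cases and 33 days in none.
- *Oral 5-ASA.* The requirement is at least 2 weeks of stable dose before randomisation. Only 5.0% of day-missing starts land 14 or more days before first dose.
- *Thiopurines, methotrexate and rectal therapy.* Protocol Sections 4.1, 4.2, 6.7.2.1 and 6.7.3 exclude these as compliant baseline treatment.

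**Where the imputed start could enter an analysis.**

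- *Prior/concomitant label:* stop date only, so unaffected.
- *Rescue:* Appendix 5 has medical reviewers classify case report form records while blinded and finalise the list before unblinding. Protocol Section 9.3.5 has ongoing medications recorded at screening and updated before dosing on Day 1, so reviewers can see what was background.
- *Biologics, parenteral glucocorticoids and procedures:* any exposure after first dose counts, so treatment that continues past first dose is caught whatever its start.
- *UC-related admissions:* Section 17.1.3 identifies them by blinded review of adverse event terms.

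**What a first-dose floor would do.** No on-treatment start would move before first dose. The mean backward shift over Days 2–85 would fall from 14.7 to 13.1 days (day missing) and from 182 to 39 days (day and month missing). In return, take true starts in the 28 days before first dose that are not documented as background and did not stop before first dose. Of these, 52.4% (day missing) and 96.0% (day and month missing) would be set to first dose.

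**Errors already run both ways.** With last dose on Day 85, 49.1% of day-missing starts on Days 86–113 move before last dose, and so out of the follow-up exemption in Appendix 5.

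**Largest effect of one missed rescue.** 1/32 = 3.1 percentage points in one arm at the planned size. SAP Section 7 says the actual size will be smaller but gives no number. Assumed arms of 20, 15 or 10 give 5.0, 6.7 or 10.0 points.

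**The case for a change.** The best argument for changing the plan needs no assumption about downstream use: an admission can be dated before the adverse event that caused it. On the enumeration above that happens in 16.4% or 88.1% of on-treatment admissions, if both dates are the same day and incomplete in the same way and the event ends on or after first dose. The appendix already distinguishes, for adverse events, a date that is "Partial, but known components show that it cannot be on or after date of first dose of study treatment", so a matching limit for medications and admissions could be written briefly. Section 13 classifies an undeterminable medication as concomitant, the worst case, and the start rule has no counterpart. The SAP also does not say whether rescue review uses recorded or imputed dates, or how a concomitant admission is defined.

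The inconsistency and the two silences stand. They do not amount to a fault that needs correcting. The conventions serve different purposes: the adverse event rule supports a treatment-emergence flag, while earliest start with latest stop brackets medication exposure. That bracketing can only lengthen a course, which makes the thresholds of more than 5 or 7 days in Appendix 5 easier to meet. A floor placed only in the last table would also leave the earliest-date rule in the prior/concomitant table untouched, so one drug record could carry two imputed starts.

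The large percentages apply to dates that should be rare. Hospitalisation makes an event serious and reportable within 24 hours, onset and resolution dates are recorded, and medications are reviewed at each treatment visit. A year-only date inside a 12-week treatment period is therefore unlikely.

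**Conclusion.** No change follows. The description of the rules is right and the arithmetic holds, but no endpoint, rescue classification or prior/concomitant label is shown to move, and no net bias is shown in either direction. For day-missing dates, apparent background use is essentially nil for oral corticosteroids and about 5% for oral 5-ASA. The larger shares need dates with the month missing as well, or wholly missing dates. A single missed rescue would cost at most 3.1 points in one arm at 32 per group. It would also require that imputed dates drive the review and that the participant otherwise met the endpoint. No hypothesis is tested (SAP Section 6.5), so no error rate is at risk.

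Which dates the reviewers use, and what makes an admission concomitant, are details that analysts can settle sensibly: classify rescue from the recorded data and date an admission consistently with its adverse event. A floor on medication starts is a debatable trade-off, not a correction.

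This rests on uniform start and first-dose dates for the percentages, on rescue review working from case report form records as Appendix 5 describes, and on incomplete dates being few, which the documents do not quantify.
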